5.2 Exclusion Criteria

Patients are excluded from the study if any of the core criteria below and any criteria from the relevant individual modules apply.

Medical Conditions

- 1 Diagnosis of post-transplant lymphoproliferative disease, Richter's transformation, Burkitt's lymphoma, Burkitt-like lymphoma, lymphoblastic lymphoma/leukaemia, chronic lymphocytic leukaemia, small lymphocytic lymphoma.
- 2 High risk of TLS according to Howard modification of Cairo-Bishop criteria and/or the presence of bulky disease (defined as any lesion ≥ 10 cm on the screening CT scan).
- 3 Unresolved toxicity from prior anticancer therapy of CTCAE Grade ≥ 2 . Patients with Grade 2 neuropathy or Grade 2 alopecia are eligible.
- 4 Active idiopathic thrombocytopenic purpura.

- 5 Active CNS involvement by lymphoma, leptomeningeal disease, or spinal cord compression. Patients with a prior history of CNS localisation of lymphoma who received treatment are eligible provided that there is no evidence of CNS involvement at study entry as documented by cerebrospinal fluid cytology and/or brain MRI.
- 6 Known history of infection with human immunodeficiency virus.
- 7 Known serologic status reflecting active hepatitis B or C infection.
 - Patients who are anti-HBc antibody positive and who are surface antigen negative will need to have a negative PCR result before enrolment. Those who are hepatitis B surface antigen positive, or hepatitis B PCR positive will be excluded.
 - Patients who are hepatitis C antibody positive will need to have a negative PCR result before enrolment. Those who are hepatitis C PCR positive will be excluded.
- 8 Known concurrent infection with CMV.
- 9 Patients must be tested for SARS-CoV-2 and those with active infection detected using either molecular or antigen tests in accordance with local testing guidelines will be excluded. Please note: Fully recovered patients (defined as no ongoing COVID-19 symptoms, except loss of sense of smell/taste) who present persistence of positive PCR test with a negative antigen test and the presence of IgG antibodies, may be included in the study.
- 10 As judged by the Investigator:
 - Any evidence of severe or uncontrolled systemic diseases, (eg, severe hepatic impairment, interstitial lung disease [bilateral, diffuse, parenchymal lung disease]).
 - Current unstable or uncompensated respiratory or cardiac conditions.
 - Uncontrolled hypertension.

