6.5.1 Permitted Concomitant Medications and Treatments

Permitted concomitant medications and treatments are listed in [Table 5](#).

Table 5 Permitted Concomitant Medications and Treatments

Supportive medication/drug class	Usage
Antiemetics (see Appendix H)	
• Permitted for the treatment of nausea and vomiting and may be administered prophylactically for recurrent events• Routine pre-medication with antiemetics for all patients is not advised
Intrathecal CNS prophylaxis	May be continued
Low-dose prednisone (≤ 10 mg) or equivalent dose of alternative	Permitted
Supportive care (including prophylactic and therapeutic anti-microbials provided they are not on the prohibited concomitant medication list [Section 6.5.2]), blood transfusions, and other medications necessary for the patient's wellbeing	May be given at the discretion of the Investigator
Erythropoietin	
• Patients already receiving erythropoietin at the time of screening for the study may continue to receive it, provided they have been receiving it for > 1 month at the time study intervention is started• Prophylactic erythropoietin should not be started before Cycle 2

Table 5 Permitted Concomitant Medications and Treatments

Supportive medication/drug class	Usage
G-CSF or GM-CSF	Primary or secondary prophylactic use of G-CSFs may be used to treat emergent neutropenia as indicated by the current ASCO guideline and according to Investigator's clinical judgement. The use of long-acting pegylated G-CSF (eg, pegfilgrastim) is not permitted during study intervention.
RANKL inhibitors and/or bisphosphonates	Permitted for the treatment of osteopenia, as recommended according to practice guidelines
Allopurinol	Mandatory for TLS prophylaxis, with dosing and schedule as per institutional guidelines
Rasburicase	Should be considered based on Appendix F and institutional guidelines
Diuretics	
 Use with care Prophylactic use should be considered only if patients have signs of volume overload
Acetaminophen (paracetamol)	Restricted to 3 grams per day or the maximum dose approved locally (if < 3 g/day) during the study
Inactivated vaccines or protein/RNA immunogen vaccines	Permitted. Note: Use of live attenuated vaccines (eg, influenza vaccine delivered as nasal spray) is prohibited
Implanted pacemaker (at study entry)	Patient is eligible at Investigator's discretion

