Appendix F Management of Specific Adverse Events

F 1 Guidance for Management of Tumour Lysis Syndrome

Tumour lysis syndrome is a known pharmacodynamic effect of antitumour therapy in haematologic malignancies including NHL. The inherent risk of TLS is dependent on the malignancy being treated and individual patient characteristics ([Coiffier et al 2008](#)).

The risk of TLS with AZD0466 in NHL patients is predicted to be highest for those with bulky disease (defined in the context of TLS as any lesion ≥ 10 cm on the screening CT scan) and elevated pretreatment lactate dehydrogenase levels, particularly in the presence of dehydration or compromised renal function.

While DLBCL, transformed lymphomas, and MCLs may be at higher risk of TLS as compared with follicular, marginal, and small cell lymphomas ([Cairo et al 2010](#)), any risk stratification based on tumour type must be considered along with the effectiveness of therapy ([Howard et al 2011](#)).

Recommendations for prophylaxis, management, dose modification, and adverse event reporting pertaining to TLS are summarised below.

F 1.1 Prophylaxis for Tumour Lysis Syndrome

Assessment of TLS risk is based on disease type, as summarised in [Table F27](#).

Table F27 Risk Assessment for Tumour Lysis Syndrome

Risk of tumour lysis syndrome		
Low Risk Disease	Intermediate Risk Disease (IRD)	High Risk Disease

• DLBCL with LDH within normal limits (WNL)• Mantle cell lymphoma with LDH WNL• Transformed lymphoma with LDH WNL• Follicular lymphoma• Hodgkin lymphoma• Marginal zone B-cell lymphoma	
• DLBCL with LDH greater than upper limit of normal (ULN) non-bulky• Mantle cell lymphoma with LDH greater than ULN non-bulky• Transformed lymphoma with LDH greater than ULN non-bulky	
• DLBCL with LDH > 2 ULN greater than ULN or bulky disease• Mantle cell lymphoma with LDH > 2 ULN greater than ULN or bulky disease• Transformed lymphoma with LDH greater than ULN and bulky disease• IRD with uric acid, potassium, and/or phosphate $>$ ULN

Renal dysfunction elevates the patient to the next risk level

DLBCL = diffuse large B-cell lymphoma; LDH: lactate dehydrogenase; MCL = mantle cell lymphoma; NHL = non-Hodgkin lymphoma; TLS = tumour lysis syndrome; ULN = upper limit of normal.

Source: Risk classification adapted from MD Anderson Cancer Center guidance.

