Prophylaxis for TLS (hydration and anti-hyperuricaemic agents) is required for all patients receiving study intervention and should be implemented according to the TLS risk level assessed for each patient (Table F27). Specific recommendations are outlined in this section, but details of management may vary per institutional practice. Patients with creatinine clearance < 80 mL/min, and patients with renal involvement from underlying disease and/or urinary outflow obstruction, may be at higher risk of TLS and complications of TLS, and should be managed accordingly. Hospitalisation may be considered for hydration management requirements at the Investigator's discretion.

Prophylaxis is summarised by TLS risk score in Table F28, according to the following principles:

- **Adequate oral fluid intake** (Table F28) is required for all patients receiving study intervention, in particular around the times of AZD0466 dosing, and patients should be encouraged to drink sufficient fluid (total of 1.5 to 2 L/day) before and after each infusion of AZD0466.
- **IV hydration** is required for patients with high risk of TLS and at Investigator's criteria. Additional IV hydration may be administered as clinically indicated in patients with diarrhoea and/or nausea and vomiting. Diuretics should be used with care and prophylactic use of diuretics should be used only if patients have signs of volume overload.
- Allopurinol (or other xanthine oxidase inhibitor) should be administered to all patients receiving study intervention and initiated at least one calendar day before the first dose of AZD0466. Allopurinol 100 to 300 mg every 8 hours is suggested, but allopurinol dose may require adjustment as described in the allopurinol prescribing information or institutional guidelines.
- **Rasburicase** should be considered as an alternative to allopurinol for patients with elevated uric acid at baseline, or high tumour burden. Rasburicase should be administered 4 hours prior to AZD0466 infusion, and as described in the rasburicase prescribing information.

Table F28 Recommended Prophylaxis for Tumour Lysis Syndrome

	Risk of tumour lysis syndrome		
	High	Intermediate	Low
Recommended prophylaxis			
Hydration	Increased hydration: oral 1.5 to 2 L/day and IV 150 to 200 mL/h Maintain urine output	From Cycle 1 Day 15: oral hydration 1.5 to 2 L/day; consider IV hydration based on risk of TLS	

Table F28 Recommended Prophylaxis for Tumour Lysis Syndrome

	Risk of tumour lysis syndrome		

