Severe (≥ 7.0 mmol/L) or symptomatic	
 As above, plus Calcium gluconate^a 100 to 200 mg/kg by slow IV infusion if concurrent ECG changes (including life-threatening arrhythmias) Regular IV insulin and dextrose, monitor blood glucose closely Consider sodium bicarbonate ^a if patient is acidaemic Consider albuterol (to be avoided in patients with acute coronary disease) Dialysis may be required
Renal dysfunction (uraemia)	
 Fluid and electrolyte management Uric acid and phosphate management Adjust doses of renally excreted medication Dialysis or haemofiltration may be required

^a Sodium bicarbonate and calcium gluconate should not be administered through the same line.

Recommended management adapted from MD Anderson Cancer Center guidance and [Coiffier et al 2008](#).

ECG, electrocardiogram; IV, intravenous.

Laboratory parameters indicating TLS (including blood urea nitrogen, creatinine, phosphate/phosphorus, uric acid, calcium, potassium, and LDH) will be evaluated. Fluid balance must be monitored per institutional standards. If more aggressive hydration management is indicated, patient hospitalisation will be considered at Investigator discretion. Allopurinol prophylaxis should be considered based on institutional guidelines.

F 1.4 Reporting Adverse Events of TLS

The Investigator will report TLS as an adverse event or serious adverse event of “laboratory TLS” or “clinical TLS” according to the classification of TLS in Appendix [G 1](#). For the purposes of adverse event reporting, a CTCAE grade for TLS should also be recorded, as follows:

- CTCAE Grade 3: TLS present
- CTCAE Grade 4: TLS with life-threatening consequences; urgent intervention indicated
- CTCAE Grade 5: Death

Tumour lysis syndrome will also be graded according to Cairo-Bishop criteria for the purposes of dose-limiting toxicity assessment and summary of adverse events of special interest (Appendix [G 2](#); [Cairo and Bishop 2004](#)).

F 2 Guidance for Management of Haematologic Changes

F 2.1 Thrombocytopenia and Haemorrhage

Platelet transfusions are permitted as per institutional standards. However, due to the mechanism of action of AZD0466, platelet transfusion may have limited efficacy within 24 to 48 hours after AZD0466 infusion.

AZD0466 should be withheld in presence of significant bleeding events with or without thrombocytopenia, such as:

- Grade 3 or 4 haemorrhage
- Any grade serious haemorrhage event

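### Table F27's high-risk lines for DLBCL and MCL each carry two LDH cut-offs and overlap the intermediate lines, and the allopurinol texts disagree, so TLS prophylaxis cannot be read one way

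*Protocol*

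**What the plan says.** **Risk level (Appendix F 1.1, Table F27).** The intermediate column lists "DLBCL with LDH greater than upper limit of normal (ULN) non-bulky" and "Mantle cell lymphoma with LDH greater than ULN non-bulky". The high-risk column lists "DLBCL with LDH > 2 ULN greater than ULN or bulky disease" and "Mantle cell lymphoma with LDH > 2 ULN greater than ULN or bulky disease". DLBCL and MCL with LDH in the normal range are low risk. Two further rules move patients up: renal dysfunction raises the level by one, and an intermediate patient with uric acid, potassium or phosphate above ULN is high risk.

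**What the level controls.** Appendix F 1.1 requires prophylaxis for everyone on treatment and ties its content to the Table F27 level. IV hydration "is required for patients with high risk of TLS" and is otherwise left to the investigator. Table F28 gives different rasburicase criteria for high and intermediate risk.

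**Allopurinol.** Section 6.5.1, Table 5: "Mandatory for TLS prophylaxis, with dosing and schedule as per institutional guidelines". Appendix F 1.1 gives it, or another xanthine oxidase inhibitor, to every treated patient from at least a day before the first dose, with rasburicase as a possible alternative for some. Appendix F 1.3: "Allopurinol prophylaxis should be considered based on institutional guidelines".

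**DLT definition (Section 10.6.6.3).** Both TLS bullets are conditional on the management the protocol recommends having been given. One covers clinical TLS of Grade 3 or above. The other covers laboratory TLS of Grade 3 or above that has not resolved within 5 days.

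**The concern.** A risk table that drives a safety measure should place each patient in one column. Here the high-risk line can be read as starting above 2 x ULN or above ULN, and the intermediate line never stops. Two sites could read the same patient's LDH, assign different levels and give different prophylaxis, each with a text to point to.

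The possible consequence for the analysis runs through Part A. A TLS event counts as a DLT under the two TLS bullets only if it happened despite recommended management, and DLTs determine the MTD (Section 10.6.6.4). If recommended management cannot be determined for a patient, whether the bullet is met can be argued either way. The allopurinol wording adds a second, independent point on which sites could differ.

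**Working it through.** No sample size, power or error rate is involved, so there is no planned figure to reproduce. The check is to apply the Table F27 lines for DLBCL and MCL to example patients.

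**Rules, with LDH as a multiple of ULN**

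- Low: LDH not above 1.
- Intermediate: LDH above 1 and non-bulky.
- High, reading A: LDH above 2, or bulky.
- High, reading B: LDH above 1, or bulky.
- High, reading C: both cut-offs together, or bulky. This equals A, because any value above 2 is also above 1.

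**Columns that each patient fits**

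| Patient | A | B | C |
|---|---|---|---|
| Non-bulky, LDH 0.8 | low | low | low |
| Non-bulky, LDH 1.5 | intermediate | intermediate and high | intermediate |
| Non-bulky, LDH 2.5 | intermediate and high | intermediate and high | intermediate and high |
| Bulky, LDH 0.8 | low and high | low and high | low and high |
| Bulky, LDH 1.5 or 2.5 | high | high | high |

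Three results follow.

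1. Between 1 and 2 x ULN, non-bulky, the answer changes with the reading.
2. Above 2 x ULN, non-bulky, two columns fit on every reading, because the intermediate line has no ceiling.
3. Bulky disease with normal LDH also fits two columns. This matters little, since exclusion 2 in Section 5.2 removes bulky disease.

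The transformed-lymphoma lines show the contrast. There the intermediate entry needs non-bulky disease and the high entry needs bulky disease, so those two lines cannot overlap.

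**Does the column change what is done?**

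- *IV hydration.* Required at high risk and discretionary otherwise (Appendix F 1.1). This applies throughout the ambiguous range. I do not rely on the hydration row of Table F28, where it is unclear which columns each cell covers.
- *Rasburicase (Table F28).* With baseline uric acid at or below 475.8 µmol/L, the criterion is two risk factors at high risk and three at intermediate risk. Take a non-bulky patient with LDH 2.5 x ULN, white cells above 50 x 10⁹/L, creatinine below the listed cut-off, and uric acid, potassium and phosphate not above ULN. LDH and white cells give 1 + 1 = 2 risk factors. The high-risk criterion is met (2 of 2 needed) and the intermediate one is not (2 of 3 needed).

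An intermediate patient already lifted to high by renal dysfunction or by raised uric acid, potassium or phosphate is high on every reading. For the rest, the level remains unsettled.

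**Allopurinol, side by side**

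| Place | Status |
|---|---|
| Section 6.5.1, Table 5 | mandatory |
| Appendix F 1.1 | every treated patient |
| Table F28 | listed at every risk level, with rasburicase as an alternative at the upper levels |
| Footnotes to Tables 13 and 14 | anti-hyperuricaemic prophylaxis required for all |
| Appendix F 1.3 | to be considered |

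Four places agree and one does not.

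**The case against.** **The doubled cut-off may be an editing remnant.** The amendment summary says Table F27 was updated for clarity, and two cut-offs side by side look like old and new text. A strike-through would be lost in plain text. This is possible, and the typeset page should be checked. However, the doubling appears in both the DLBCL and the MCL line. Removing either cut-off also leaves the intermediate line without a ceiling, so the overlap above 2 x ULN remains.

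**A sensible reader would take the highest level that fits.** Perhaps, but the table states no such rule. Under reading B that convention would also leave the intermediate DLBCL and MCL lines with nobody in them.

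**A reader might infer that the table firmly puts the patient at 1 to 2 x ULN in both columns.** It does not. That follows only if the lower cut-off is the operative one. What can be said is that the level is undetermined.

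**A reader might also infer that Table F27 decides who is enrolled.** The documents do not support this. Exclusion 2 begins "High risk of TLS according to" and then names a published TLS classification, with bulky disease as the other ground. It does not cite Table F27, which credits a different source. Appendix G uses the named classification to define and grade TLS. Whether it also contains a pre-treatment risk scale cannot be seen from the documents.

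**The DLT effect is limited.** Appendix F 1.1 accepts that management details vary by institution, and Section 10.6.6.3 lets the Safety Review Committee judge other toxicities to be DLTs. This stands. The ambiguity could make attribution disputable, but it does not by itself change any patient's DLT status.

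**The allopurinol conflict is narrow.** It rests on one sentence in a section about treating TLS, and it has nothing to do with LDH. Both points are right. The sentence nevertheless speaks of prophylaxis, so it does contradict Table 5 and F 1.1.

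**Conclusion.** Wrong as written. The high-risk DLBCL and MCL lines in Table F27 give two incompatible LDH cut-offs, and the intermediate lines have no upper limit. The level of a non-bulky patient between 1 and 2 x ULN cannot be determined, and a non-bulky patient above 2 x ULN fits two columns whichever cut-off was meant. Because prophylaxis follows the level, sites may prevent TLS differently, and DLT attribution could be disputed. The allopurinol conflict is real but separate and confined to one sentence.

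The conclusion rests on the table's wording as it reads in the text. If the typeset page shows one cut-off struck out, the first part may fall away and the second remains. The number of patients affected cannot be stated: the documents give no LDH distribution, and the cohort sizes are redacted. No effect on eligibility is claimed.

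**What to change.** The sponsor should:

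1. Reconcile the LDH entries for DLBCL and MCL in Table F27 so that every patient falls in exactly one column. This means settling the cut-off in the high-risk lines and stating where the intermediate lines end.
2. Reconcile Table 5, Appendix F 1.1 and Appendix F 1.3 on allopurinol, so that its status reads the same in all three.

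The thresholds and the allopurinol rule are the sponsor's clinical decision, and none is proposed here. The cost is a few lines of protocol wording and telling sites about it. Sample size, endpoints and analyses are unaffected.

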10.6.6 Dose Modification and Toxicity Management

10.6.6.1 Starting Dose, Dose Escalation Scheme and Stopping Criteria

The dose escalation part of Module 1 (Part A) will enrol up to approximately ^{CC1} DLT evaluable patients with at least ^{CC1} DLT evaluable patients at each dose level. During Part A, up to ^{CC1} patients may be enrolled per dose level. The structure of the dose escalation part is shown in [Figure 3](#).

Figure 3 **Module 1 Part A Dose Escalation Schema**

^a Alternative dosing schedule: option of dose reduce and/or change in dosing schedule from weekly to every 2 weeks based on emerging safety data.

B-NHL = B-cell non-Hodgkin lymphoma; DL = dose level; MTD = maximum tolerated dose; R/R = relapsed/refractory.

Initial dose levels will be set according to nonclinical modelling and data from Studies D8240C00003 and D8241C00001 with an intra-patient dose ramp-up to mitigate the risk of TLS. The intra-patient ramp-ups will involve beginning at a specified lower dose and rapidly increase the dose to reach target value by Day 8. For example, in dose level 1, at Cycle 1 Day 1 AZD0466 will be administered at 150 mg followed by 300 mg at Cycle 1 Day 4 and reaching target dose of 600 mg at Cycle 1 Day 8. Thereafter, weekly dosing would continue at 600 mg. Each cycle is 28 days with Cycle 1 consisting of ramp-up to achieve the target dose level and then 3 doses at target level on Days 8, 15, and 22 with a 28-day DLT period (see Section 10.6.6.3).

The intra-patient dose escalation scheme and/or dose schedule for each cohort may be modified based on safety, PK, and pharmacodynamic findings of a previous dose level. If a dose level is declared not tolerated due to liver toxicity or cytopenias, the same dose level may be tested at a 2-weekly dosing schedule. Dose escalation from this point will be on a 2-weekly dosing schedule. Should the SRC determine this dose is not tolerated on a 2-weekly dosing schedule, the weekly dose level below will be considered the MTD.

The decisions on the adequacy of the dose escalation portion of the design were based on outcomes from an internal AstraZeneca simulation package which calculates estimates of the likelihood of selecting the true MTD under a range of different scenarios. Operating characteristics are presented in [Table 15](#).

Table 15 Decision Rules Based on mTPI-2 for Dose Escalation

CCI

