	High	Intermediate	Low
Anti-hyperuricemics	Allopurinol 100 to 300 mg every 8 hours Early consideration of rasburicase ^a as an alternative, based on baseline uric acid and tumour burden		Allopurinol 100 to 300 mg every 8 hours
Criteria for use of rasburicase			
Serum uric acid at baseline	> 475.8 µmol/L ^b + 1 risk factor ≤ 475.8 µmol/L ^b + 2 risk factors	> 475.8 µmol/L ^b + 2 risk factors ≤ 475.8 µmol/L ^b + 3 risk factors	NA
Risk factors	Serum creatinine > 1.3 mg/dL (> 88.4 µmol/L) WBC > 50 × 10 ⁹ /L LDH > 2 × ULN		NA

^a Rasburicase is contraindicated in patients with glucose-6 phosphate dehydrogenase deficiency, known hypersensitivity to rasburicase, haemolytic anaemia or methemoglobinemia

^b Uric acid cutoff may be adjusted according to local guidance.

Recommended prophylaxis adapted from MD Anderson Cancer Center guidance ([Coiffier et al 2008](#)) and Cairo and Bishop ([Cairo and Bishop 2004](#)).

IV = intravenous; LDH = lactate dehydrogenase; TLS = tumour lysis syndrome; WBC = white blood cell.

F 1.2 AZD0466 Dose Modifications for Tumour Lysis Syndrome

AZD0466 dose modifications for TLS are summarised in [Table F29](#).

Table F29 AZD0466 Dose Modifications for Tumour Lysis Syndrome

Abnormality	Action with AZD0466
Laboratory findings (serum)	
Uric acid ≥ 475.8 µmol/L	
 Initiate supportive therapy as per standard clinical practice, additional guidance provided in Table F30.
Potassium ≥ 6.0 mmol/L	
Phosphate ≥ 1.6 mmol/L (5.0 mg/dL) with ≥ 0.16 mmol/L (0.5 mg/dL) increase ^a	
 Delay AZD0466 for up to 7 days (if finding present before administration of AZD0466) If resolution to within specified threshold in ≤ 7 days, restart at the same dose level If resolution after 7 days restart AZD0466 at one lower dose
Corrected calcium < 1.75 mmol/L	
Creatinine increase by > 26.5 µmol/L from baseline (creatinine > 1.5 × ULN if no baseline)	
All laboratory abnormalities must resolve to within specified threshold before AZD0466 is restarted	
Clinical findings	
Signs suggestive of clinical TLS (eg, acute kidney injury, cardiac arrhythmia/dysrhythmia ^b , hypotension ^c , heart failure ^c)	
 Initiate supportive therapy as per standard clinical practice Delay AZD0466 for up to 14 days AZD0466 at one lower dose following resolution

Table F29 AZD0466 Dose Modifications for Tumour Lysis Syndrome

Abnormality	Action with AZD0466

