5.6.8 Tumour lysis syndrome

5.6.8.1 Definitions and Derivations

Tumour lysis syndrome (TLS) is an important identified risk for AZD0466. TLS prophylaxis is mandatory for all patients starting 3 days before the first dose of AZD0466, which should be followed in addition to institutional guidelines.

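### Table F28 gives the rasburicase creatinine cut-off in two units that do not agree, and its hydration row does not match the F 1.1 text for the doses before Cycle 1 Day 15

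*Protocol*

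**What the plan says.** Appendix F 1.1 of the protocol sets out TLS prophylaxis in text and then tabulates it by High, Intermediate and Low risk in Table F28.

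- **Oral fluids, text.** Adequate intake "is required for all patients receiving study intervention, in particular around the times of AZD0466 dosing". The amount and timing are given as "total of 1.5 to 2 L/day) before and after each infusion of AZD0466".
- **IV fluids, text.** Required for patients at high TLS risk, and otherwise left to the Investigator.
- **Hydration row, Table F28.** The first cell reads "Increased hydration: oral 1.5 to 2 L/day and IV 150 to 200 mL/h" and carries no start day. The second reads "From Cycle 1 Day 15: oral hydration 1.5 to 2 L/day; consider IV hydration based on risk of TLS".
- **Rasburicase criteria, Table F28.** There are three risk factors: white cells above 50 × 10⁹/L, LDH above 2 × ULN, and a creatinine factor printed as "Serum creatinine > 1.3 mg/dL (> 88.4 µmol/L". In the High column one factor is needed if baseline uric acid exceeds 475.8 µmol/L and two if it does not. In the Intermediate column the numbers are two and three. The Low column is marked not applicable.
- **Dosing, Section 10.6.6.1.** For dose level 1, "at Cycle 1 Day 1 AZD0466 will be administered at 150 mg followed by 300 mg at Cycle 1 Day 4", then the target dose on Days 8, 15 and 22.
- **Schedule of Activities, Table 13.** TLS prophylaxis is marked on all five of those days, and a note makes hydration and anti-hyperuricaemic agents mandatory for everyone treated.
- **Lead-in.** The protocol wants allopurinol "initiated at least one calendar day before the first dose of AZD0466". SAP 5.6.8.1 says "TLS prophylaxis is mandatory for all patients starting 3 days before the first dose of AZD0466".

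**The concern.** A bracketed SI value should be the same threshold in other units. Here it is not, so the result of the criterion depends on the unit in which the local laboratory reports. The hydration row is tied to Day 15, but the ramp-up to target dose, which the protocol uses to limit TLS risk, is complete by Day 8. On its face the table is silent, or says something different from the text, for those doses.

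TLS is an adverse event of special interest. Both TLS entries in the dose-limiting toxicity (DLT) definition (Section 10.6.6.3) depend on the event occurring, or failing to resolve, despite the management that the protocol recommends. When that recommendation can be read two ways, so can the condition. In Part A, DLT counts drive the mTPI-2 decisions and the choice of MTD.

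**Working it through.** **1. Creatinine.** The inputs are the printed pair, 1.3 mg/dL and 88.4 µmol/L. The documents give no conversion factor, so I assume the one that follows from a molar mass of 113.12 g/mol:

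µmol/L = mg/dL × 10 / 113.12 × 1000 = mg/dL × 88.40

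- 1.3 × 88.40 = 114.9 µmol/L, so the printed 88.4 is not reproduced.
- 88.4 / 88.40 = 1.00 mg/dL. The bracketed value is the conversion of 1.0, not of 1.3.
- Gap: 114.9 − 88.4 = 26.5 µmol/L, or 0.30 mg/dL, a ratio of 1.30.
- Range: rounding the factor to 88 gives 1.3 × 88 = 114.4. For the printed pair to agree, the factor would have to be 88.4 / 1.3 = 68.0.

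As a check on the method, the same approach turns uric acid of 8.0 mg/dL into 475.9 µmol/L, against 475.8 in Table G31. That pair does reproduce.

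**2. Can the band matter?** Table 3 admits creatinine up to 1.5 × ULN, or clearance of at least 50 mL/min. On the creatinine route alone, part of the band is admissible when the local ULN is above 88.4 / 1.5 = 58.9 µmol/L, and all of it when the ULN is at least 114.9 / 1.5 = 76.6 µmol/L.

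For a patient in the band, creatinine decides the result when the other two factors (white cells, LDH) fall exactly one short:

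| Column | Uric acid (µmol/L) | Factors needed | Creatinine decides if other factors present = |
|---|---|---|---|
| High | > 475.8 | 1 | 0 |
| High | ≤ 475.8 | 2 | 1 |
| Intermediate | > 475.8 | 2 | 1 |
| Intermediate | ≤ 475.8 | 3 | 2 |

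So the mismatch can change the result in each of the four cells, but only for patients at that margin.

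**3. Hydration.** Cycle 1 doses fall on Days 1, 4, 8, 15 and 22. Those before Day 15 are Days 1, 4 and 8: three of five, namely both ramp-up doses and the first target dose. The column span of the second cell is not certain in the text I have, so I take each reading in turn.

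- *The cell covers Intermediate and Low risk (or Intermediate only).* The table then gives these patients no hydration at Days 1, 4 and 8. The text and Table 13 do.
- *The row is split by time, with the first cell for everyone until Day 15.* The table then lists IV fluid at 150 to 200 mL/h for all risk groups, more widely than the text requires.

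Neither reading agrees with the text.

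**4. Lead-in.** One calendar day is a minimum and applies to allopurinol. A start three days before dosing satisfies both documents. SAP 5.6.8.2 plans listings and a key-patient table for TLS, and none of them uses the lead-in.

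**The case against.** The strongest reply is that the protocol already says what to do on Days 1, 4 and 8. The text asks for fluids around each infusion, the schedule marks prophylaxis on those days, and the table only summarises. F 1.1 also lets management details vary with institutional practice, and rasburicase is something to consider rather than a fixed entitlement. Much of this stands: a site that reads the text and schedule will hydrate from Day 1. It does not remove the conflict, because a table that disagrees with the text it summarises still needs correcting. The schedule's note also sends the reader to F 1.2, which covers dose modification, not to F 1.1.

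Four stronger inferences are tempting, and the documents do not support them.

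- *Prophylaxis does differ between sites.* It can. Nothing shows that it does, and allopurinol before the first dose is asked of every patient, so the early gap concerns hydration only.
- *The Day 15 cell governs most enrolled patients, because high TLS risk is an exclusion.* Core exclusion 2 uses the Howard modification of the Cairo-Bishop criteria and bulky disease. Table F27 classifies differently: for example, it also places non-bulky mantle cell lymphoma with LDH above 2 × ULN under High. The share in each column is not known.
- *The same event will be a DLT at one site and not at another.* Any Grade 5 event is a DLT, and the Safety Review Committee can judge other toxicities to be DLTs. That central review limits discordance.
- *The SAP contradicts the protocol by two days.* As shown above, the two lead-ins are compatible.

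**Conclusion.** Two errors in Table F28 stand. The creatinine cut-off is wrong as printed: the two values differ by 26.5 µmol/L (0.30 mg/dL, a ratio of 1.30), and patients between them are classified by reporting unit. This reaches only High- and Intermediate-risk patients at the margin of the factor count, at whatever time the criterion is applied. The hydration row conflicts with the F 1.1 text for three of the five Cycle 1 doses on either reading of its layout, and on the reading by risk group it also leaves a gap where the schedule marks prophylaxis.

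The consequence is ambiguity in safety guidance on which the TLS DLT criteria rely. It is not a demonstrated difference in care or in DLT counts. The creatinine result assumes the standard molar mass, and the hydration result assumes that the extracted cell text is complete. The SAP lead-in is a wording matter only.

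**What to change.** - **Creatinine.** State one cut-off in Table F28, with a bracketed value that is its true conversion. Which threshold is meant is the sponsor's decision.
- **Hydration.** Check the column span of the row in the source PDF. Then reconcile the row with the F 1.1 text and Table 13, so that each risk column says what applies on Days 1, 4 and 8 as well as from Day 15. The content of each cell is again the sponsor's clinical choice.
- **Minor.** Align the lead-in wording in SAP 5.6.8.1 with the protocol.

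The cost is an edit to one protocol table and one SAP sentence. No procedure, data item or analysis is added.
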